9.3.1. Relationship of AE to Study Medication

The relationship of an adverse event to study medication is to be assessed according to the following definitions:

- **Definitely Related:** Strong evidence exists that the study drug caused the adverse event. There is a temporal relationship between the event onset and administration of the study drug. There is strong therapeutic and pharmacologic evidence that the event was caused by the study drug. The subject's clinical state or concomitant therapies have been ruled out as a cause. In the case of cessation or reduction of the dose, the event abates or resolves, and reappears upon re-challenge.
- **Probably Related:** A temporal relationship exists between the event onset and the administration of study drug, and appears with some degree of certainty to be related based on the known therapeutic and pharmacologic actions of the study drug. It cannot be readily explained by the subject's clinical state or

concomitant therapies. In the case of cessation or reduction of the dose, the event abates or resolves.

- **Possibly Related:** A temporal relationship exists between the event onset and the administration of study drug. Although the adverse event may appear unlikely to be related to the study drug, it cannot be ruled out with certainty; and/or the event cannot be readily explained by the subject's clinical state or concomitant therapies.
- **Not Related:** Evidence exists that the adverse event definitely has an etiology other than the study drug (eg, pre-existing condition or underlying disease, intercurrent illness, or concomitant medication) and does not meet any criteria listed above.

Included in the description should be the nature of the sign or symptom; the date of onset; date of resolution (duration); the severity; the relationship to study treatment or other therapy; the action taken (if any), and the outcome.

9.3.2. Unexpected Adverse Event

An unexpected adverse event is one not previously reported (in nature, severity or incidence) in the current PI's Brochure, in the clinical plan, or elsewhere. Unexpected, as used in this definition, refers to an adverse drug experience that has not been previously observed (eg, included in the PI Brochure) rather than from the perspective of such experience not being anticipated from the pharmacological properties of the pharmaceutical product.

All adverse events must be recorded in the case report form (CRF). To avoid colloquial expressions, the adverse event should be reported in standard medical terminology and will be coded in MedDRA. Whenever possible, the adverse event should be evaluated and reported as a diagnosis rather than as individual signs or symptoms. If a definitive diagnosis is not possible, the individual symptoms and signs should be recorded. Any laboratory abnormalities deemed clinically significant by the PI should be reported on the adverse event CRF. Whenever possible, the etiology of the abnormal findings will be documented on the CRF. Any additional relevant laboratory results obtained by the PI during the course of this study will be supplied to the sponsor and recorded on the CRF. The required SAE information should also be completed on the CRFs and the data reported within 24 hours from the time that the event was identified. This will ensure that the written documentation is transmitted to the appropriate pharmacovigilance contact person within the required reporting time period.

The IRB/regulatory authority must be informed if the SAE or AE, in the opinion of Tosk or the PI, is likely to affect the safety of the subjects or the conduct of the study.

All Investigators participating in the trial will also be notified of any unexpected SAEs determined to be related to study treatment.

For any questions about adverse events or serious adverse events contact Sponsor's medical monitor

9.4. WARNINGS AND PRECAUTIONS

Subjects receiving study therapy (TK-112690) should be monitored by a physician experienced in the use of cancer chemotherapy agents. Use of these agents in pregnant or breast-feeding women is contraindicated.

9.4.1. Precautions

Infusion reactions with the first dose of TK-112690 may be observed. TK-112690 administration should be interrupted in all subjects with severe infusion reactions and appropriate medical therapy administered.

9.4.2. Treatment Failure

In case of treatment failure, patients will be treated using the Standard Guidelines for Management of Mucositis.⁹¹

9.5 EFFICACY ASSESSMENTS

9.5.1 Mucositis Assessment Scales

The scales described in **Section 20.6** of this protocol will be used to assess/rate mucositis. The scales are OMAS/Sonis,^{92,93} PROMS,⁹⁴ WHO and CTCAE/mucositis.

Response

Response will be determined according to the RECIST methodology. It will be the best response recorded from the start of the treatment until disease progression/recurrence. To be assigned a status of partial response or complete response, changes in tumor measurements must be confirmed by repeat assessments performed at least 4 weeks after the criteria of response are first met.

Target lesions

• Complete response is defined as the disappearance of all target lesions.

⁹¹Rubenstein EB, Peterson DE, Schubert M, Keefe D,McGuire D, Epstein J, EltingLS,Fox PC, Cooksley C, Sonis ST. Clinical Practice Guidelines for Mucositis. Cancer 2004;100 (9 Suppl):2026–2046.

⁹²Sonis ST, Eilers JP, Epstein JB, LeVeque FG, Liggett WH Jr, Mulagha MT, Peterson DE, Rose AH, Schubert MM, Spijkervet FK, Wittes JP. Validation of a new scoring system for the assessment of clinical trial research of oral mucositis induced by radiation or chemotherapy. Mucositis Study Group. Cancer.1999; 85: 2103-13.

⁹³Oral mucositis and the clinical and economic outcomes of hematopoietic stem-cell transplantation. Sonis ST, Oster G, Fuchs H, Bellm L, Bradford WZ, Edelsberg J, Hayden V, Eilers J, Epstein JB, LeVeque FG, Miller C, Peterson DE, Schubert MM, Spijkervet FK, Horowitz M.

J ClinOncol.2001 ;19:2201-5.

⁹⁴ Kushner JA, Lawrence HP, Shoval I, Kiss TL, Devins GM, Lee L, Tenenbaum HC, Development and validation of a Patient-Reported Oral Mucositis Symptom (PROMS) scale. J Can Dent Assoc. 2008; 74: 59.

- Partial response is defined as at least a 30% decrease in the sum of the longest diameter of the target lesions, taking as a reference the baseline sum longest diameter.
- Progressive disease is defined at least a 20% increase in the sum of the longest diameter of target lesions, taking as a reference the smallest sum longest diameter recorded since the treatment started or the appearance of one or more new lesions.
- Stable disease is defined as shrinkage insufficient to qualify for partial response or insufficiently increased to qualify for progressive disease, taking as a reference the smallest sum longest diameter since the treatment started.

Non-target lesions

- Complete response is defined as the disappearance of all non-target lesions.
- Non-complete response /non-progressive disease is defined as persistence of 1 or more non-target lesion.
- Progressive disease is defined as the appearance of 1 or more new lesions and/or unequivocal progression of existing non-target lesions.
- The cytological confirmation of the neoplastic origin of any effusion that appears or worsens during treatment when the measurable tumor has met criteria for response or stable disease is mandatory to differentiate between response or stable disease and progressive disease.

Confirmation of No Response on Tumor

To be assigned a best tumor response status of partial response or complete response, changes in tumor measurements in subjects with responding tumors must be confirmed by repeat studies that should be performed no less than 4 weeks after the criteria for response are first met. In the case of stable disease, follow-up measurements must have met the stable disease criteria at least once after study entry at a minimum interval of 8 weeks.

Determination of Overall Best Tumor Response by RECIST (Version 1.1) Methodology

The overall assessment of best tumor response will involve all parameters as depicted in Table 13below.

Target lesions [*]	Non-Target lesions ^{**}	New Lesions***	Overall Response	
Complete Response	Complete Response	No	Complete response	
Complete Response	Non-complete Response /Non-progressive disease	No	Partial response	
Partial Response	Non-progressive disease No		Partial response	
Stable disease	Non-progressive disease	No	Stable disease	
Partial disease	Any response	Yes or No	Progressive disease	
Any response	Progressive disease	Yes or No	Progressive disease	
Any response	Any response	Yes	Progressive disease	

Table 13. Tumor response criteria

May include measurable lesions not followed as target lesions or non-measurable lesions

***Measurable or non-measurable lesions

The overall best tumor response is the best response recorded from the start of the treatment until disease progression/recurrence, taking as reference for tumor progression the smallest measurements recorded since the treatment started. The subject's best tumor response assignment will depend on the achievement of both measurement and confirmation criteria.

Subjects will be defined as being not evaluable for response (NE) if there is no post-baseline lesion assessment, unless the subject terminates from the study for disease progression.

Subjects with a global deterioration of health status requiring discontinuation of treatment without objective evidence of disease progression at that time should be reported as "symptomatic deterioration" on the Study Termination CRF. Every effort should be made to document the objective progression even after discontinuation of treatment. It should also be noted that a tumor marker increase does not constitute adequate objective evidence of tumor progression. However, such a tumor marker increase should prompt a repeat radiographic evaluation to document whether or not objective tumor progression has occurred. In some circumstances, it may be difficult to distinguish residual disease from normal tissue. When the evaluation of a CR depends upon this determination, it is recommended that the residual lesion be investigated by fine needle aspirate or biopsy before confirming the CR status.

9.5.3. Surrogate Markers

The effect of TK-112690 treatment on mucositis-related inflammatory markers such as CD40/CD40L will be studied. The results of the exploratory assessments will not be recorded in the CRF but will be reported separately in an addendum.

9.5.4. Surrogate Markers

Plasma samples for establishing the surrogate marker profiles will be obtained at times specified in the protocol. The results of the exploratory assessments will not be recorded in the CRF but will be reported separately in an addendum.

9.6 APPROPRIATENESS OF MEASUREMENTS

Study measurements are those associated with a standard evaluation of a new modality for modifying side-effects associated with chemotherapy.

10.0. STATISTICAL CONSIDERATIONS

10.1. GENERAL CONSIDERATIONS

All analyses will be performed. and all **Tables**, **Figures**, and data listings will be prepared using a validated statistical program. Summary statistics for continuous variables will include the mean, standard deviation, median, minimum, and maximum value; categorical variables will be presented as counts and percentage.

10.1.1. Sample Size and Associated Power

The primary objective of this Phase 2a trial is to evaluate the pilot efficacy and the safety/tolerability of MetrexassistTM administered intravenously to subjects with cancer also receiving 45 mg/m² MTX. This is

an exploratory study and is may not be powered to demonstrate statistical significance. The sample size is based not on statistical calculations but on the outcome in the Phase 1b study where all patients received TK-112690 experienced relatively little mucositis. Without the TK-112690 considerably more mucositis is expected, perhaps enough to achieve statistical significance. At a minimum, sufficient data will be obtained to accurately power the next study with TK-112690 and MTX.

10.1.2. Randomization of the Trial

The clinical CRO or a third-party provider will alternatively assign patients as per the randomization list. If a patient drops out of the study before completing first dosing, he/she will be replaced by someone with the same assigned treatment.

10.2. POPULATIONS

10.2.1. Efficacy and Safety Population

The efficacy population will consist of all subjects who received at least four doses of TK-112690. The safety population will consist of all subjects who receive at least one dose of TK-112690.

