Title of the Study

A Phase 2a, Multi-center, Placebo-controlled, Randomized, Partially Blinded, Study of Infused METREXASSISTTM (Parenteral TK-112690) or MetrexassistTM Placebo Administered Along with Methotrexate Weekly for Four Consecutive Weeks to Patients with recurrent or residual SCCHN.

Principal Investigators Approximately 3

Study Centers Approximately 3

Clinical Phase

Phase 2a

Number of Subjects

The total number of individuals enrolled will be 22, 11 dosed TK-112690 and methotrexate and 11 patients dosed methotrexate and placebo. All patients will be dosed a nutritional supplement to assure adequate basal levels of uridine and uridine-related biochemicals.

Study Drug:TK-112690, an anhydrouridine inhibitor of uridine phosphorylase

Projected Subject Enrollment Duration

10 months

Objectives

Primary

Determine pilot efficacy of an iv infusion of TK-112690 to placebo as a mucositis preventive in subjects with locally advanced, residual, or recurrent or metastatic SCCHN scheduled to receive MTX as chemotherapy.

Secondary

Confirmation of the safety/tolerability of a continuous administered weekly for 4 weeks and lowering of plasma concentrations of surrogate markers of mucositis, e.g., CD40/CD40L, post TK-112690 in patients

suffering from local, advanced, residual or recurrent, metastatic SCCHN receiving sequential continuous iv infusions of TK-112690 and MTX or TK-112690 placebo and MTX.

Study Design

A Phase 2a, Multi-center, Placebo-controlled, Randomized, Partially Blinded, Study in Patients with recurrent or residual SCCHN.

Patients will receive MTX at a dose of 45 mg/m² administered weekly for **4 consecutive weeks** as an iv infusion along with a nutritional supplement containing uridine monophosphate (Fortasyn ConnectTM / SouvenaidTM, Nutricia NV) administered two hours before the MTX. One hour before the MTX treatment the patients will be administered the first infusion of the day of either TK-112690 or placebo depending on randomization infusion. Five hours after the MTX treatment the patients will be administered the second treatment of either TK-112690 or placebo depending on randomization. The TK-112690 dose will be 45 mg/kg.

- A total of 22 patients will be enrolled into one of 2 different dose groups: TK-112690 treated or placebo treated.
- Screening must be within 15 days of subject enrollment.
- Patients will remain for observation at the clinical site for a minimum of 25 hours post initial TK-112690 or placebo dose.

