- Subjects that have participated in any other investigative clinical trial in the past 4 weeks.

Dose and Dosing Regimen

The dose of METREXASSISTTM (TK-112690) will be 45 mg/kg administered parenterally over one hour in a clear, neutral, aqueous formulation (no organic chemical excipients). METREXASSISTTM will be given one hour before and 5 hours after the MTX treatment. The nutrient drink will be given one hour before METREXASSISTTM infusion. The MTX formulation will that traditionally used as standard-of-

care at a study site.

Test Product, Dose and Mode of Administration

- METREXASSISTTM (TK-112690 for Infusion) is a clear, sterile, neutral (pH=7.4), aqueous solution containing 5 mL of 100 mg/mL TK-112690.
- METREXASSISTTM is packaged as a 5 mL solution in a 10 mL flint glass vial with an elastomeric stopper held in place by an aluminum seal and flip-off cap. The concentration of TK-112690 in the solution is 100 mg/mL
- METREXASSISTTM will be administered as a continuous iv infusion over a duration of one hour in a volume of 250 mL normal saline.
- The nutrient drink, Fortasyn Connect[™] / Souvenaid[™], is commercially available as a 125 mL, 125 kcal solution. The drink is administered orally.
- The placebo is isotonic saline.

Reference Therapy or Comparator

Placebo-Isotonic saline

Follow-up

[figure not shown]
Subjects need to return at Day 1 of Week 6, which is two weeks from the last dose of the study drug.

Statistical Methods

- Safety: AEs, vital signs, physical examination data and clinical laboratory data will be analyzed using descriptive statistics with safety outcomes for patients in a dose group pooled & compared with patients in other groups.
- Mucositis: Scale data from individual doses groups will be analyzed using descriptive statistics.
- Surrogate Markers: Plasma concentration data evaluated for individual doses groups using descriptive statistics as well as compared with Surrogate marker data from the completed Phase 1bstudy.

INTRODUCTION

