2.0. STUDY OBJECTIVES

2.1. PRIMARY OBJECTIVE

The primary objective of this study is to establish pilot efficacy compared to placebo for TK-112690 as an anti-mucositis agent when administered weekly for 4 weeks by iv infusion to subjects with locally advanced, residual or recurrent or metastatic SCCHN scheduled to receive MTX as chemotherapy.

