3.5. RANDOMIZATION AND BLINDING

The Phase 2a study will be partially blinded. The patient and investigator will be blinded as to whether TK-112690 or placebo is administered. The CRO, sponsor, and site pharmacist will know whether the patient was administered active drug or placebo.

A list providing randomization, active drug and placebo, for each of the 22 subjects will be prepared (List A). Another list will provide randomization for 8 additional subjects if additional subjects are enrolled (List B). Both lists will be kept by the CRO.

A designated person or Pharmacist will prepare the TK-112690 treatments by adding either active drug or placebo into 250 ml 0.9% sodium chloride iv bottle (**Appendix 3**). Whether active drug or placebo is added will reflect the subject number and the randomization suggestion made in the Randomization List for that subject number. The CRO will provide the designated person or pharmacist with vials re-labelled to maintain the partial blind. The randomization will be done by the CRO or a third-party vendor.

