5.2. STUDY THERAPY ADMINISTRATION

The study therapy will be administered as an infusion via a peripheral vein in the forearm delivered using a catheter. This access vein for the infusion must not be used for blood sampling. Replacement of the intravenous catheter will be done according to local practice and the discretion of PI or designee, e.g., in the event of phlebitis. If a catheter is replaced, it should be flushed with saline prior to removal unless there are signs of phlebitis. TK-112690/placebo will initially be administered as a one-hour infusion. In case of immediate adverse reaction to the infusion, please follow management of reaction (Appendix 4: Infusion Reaction Criteria).

Epinephrine (1:1000) for subcutaneous injection, diphenhydramine (12.5 mg to 50 mg) for iv injection, and any other medications and resuscitation equipment for the emergency management of anaphylactic reactions must be available in the room where the infusions are being performed.

All patients will be evaluated at a follow-up visit on Day 1 of Week 6 post after initial drug treatments.

METREXASSISTTM (TK-112690 for Injection) should be prepared for infusion by a healthcare professional using aseptic technique. METREXASSISTTM will be diluted into 250 mL of 0.9% sodium chloride in a iv bag/bottle. Please refer to **Appendix 3** for the directions on how to calculate and dilute for the different doses to be administered to the subjects.

For the placebo will be prepared as described above for the TK-112690 except isotonic saline in 10 mL glass vials will be substituted for the 10 mL METREXASSISTTM vials.

Dosing will be calculated on a mg/kg basis and rounded to the closest 10 mg. The TK-112690/placebo dose will be 45 mg/kg.

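### Section 10.2.1 counts only doses of TK-112690, so as written both analysis sets leave out all 11 placebo patients; the four-dose efficacy rule also has no stated unit

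*Combined protocol and SAP*

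**What the plan says.** Section 10.2.1 holds the plan's only analysis-set definitions. For efficacy: "The efficacy population will consist of all subjects who received at least four doses of TK-112690". For safety: "The safety population will consist of all subjects who receive at least one dose of TK-112690". Neither mentions placebo, and no intention-to-treat, all-randomised or per-protocol set appears elsewhere.

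The rest of the plan is a two-arm comparison:

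- Section 2.1: "The primary objective of this study is to establish pilot efficacy compared to placebo for TK-112690 as an anti-mucositis agent".
- Synopsis, Number of Subjects: "11 dosed TK-112690 and methotrexate and 11 patients dosed methotrexate and placebo".
- Synopsis, Statistical Methods: "safety outcomes for patients in a dose group pooled & compared with patients in other groups". Sections 10.3 and 10.3.1 likewise summarise safety by treatment group.

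Placebo is isotonic saline (Synopsis; Sections 1.7.2 and 5.1.2).

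The study infusion is given twice on each treatment day, before and after methotrexate (Sections 1.7.1 and 7.1.3), weekly for four weeks.

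**The concern.** Read as an instruction to a programmer, Section 10.2.1 removes the control arm from both sets. The comparison in Section 2.1 and the by-group safety tables could not then be produced. Section 10.1.1 expects the data to power the next study. It names no set, but the only efficacy set defined would contain no control patients.

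Adding placebo to the wording leaves a second problem. A patient enters the efficacy set only by staying on treatment for four doses, which is a condition observed after randomisation and tied to toxicity. Section 3.1.2 withholds treatment after grade 3 or 4 events. Section 8.2 allows withdrawal for intolerable toxicity or for a toxicity delay of more than two weeks. Mucositis is itself graded by CTCAE (Appendix 6), so the outcome could influence who is analysed.

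The rule also has no unit. The sponsor and CRO know the allocation (Sections 3.5 and 5.5), so an open unit could be settled later by people who know who received what.

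**Working it through.** **Plan's own figure.** Section 10.1.1 says the sample size does not rest on a statistical calculation, so there is no power figure to reproduce. The allocation adds up: 11 + 11 = 22.

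**1. Applying the rules as written.** A saline patient receives 0 doses of TK-112690, which is below 1 and below 4.

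| Set | Active | Placebo |
|---|---|---|
| Safety (at least 1 dose of TK-112690) | at most 11 | 0 |
| Efficacy (at least 4 doses of TK-112690) | at most 11 | 0 |

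The planned patients left out of each set number at least 11 of 22, or 50%.

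**2. The unit.** Two infusions per treatment day × 4 weeks = 8 infusions per patient.

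- If a dose is one infusion, 4 / 2 = 2 treatment days, so the fourth falls on Day 1 of Week 2 when dosing runs to schedule. Section 1.5.2.1 uses the word this way for Phase 1b, and Appendix 3 calculates the dose for a single bag.
- If a dose is one weekly treatment, four doses means all 8 infusions. The Phase 1b figure captions in Section 1.5.2.11 point this way: they describe patients who completed four doses and then list four intervals, one per study week. On this reading a patient must also pass the tolerability check after Week 2 in Section 10.3.

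**3. How many patients each unit keeps, once placebo is included.** The proxy is the number of Phase 1b patients with a BMI value in that week (Table 9; 15, 30, 45 and 60 mg/kg cohorts in order):

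- Week 1: 3 + 3 + 4 + 15 = 25
- Week 2: 3 + 3 + 3 + 14 = 23
- Week 4: 3 + 3 + 2 + 10 = 18

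Cross-check: the vital-sign rows of Table 9 carry two readings per patient per week (Week 1: 50 = 2 × 25). Week 2 is 6 + 6 + 6 + 28 = 46 = 2 × 23. Week 4 is 6 + 6 + 4 + 20 = 36 = 2 × 18. The two sources agree.

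| Unit | Phase 1b proxy | Exact (Clopper-Pearson) 95% interval | × 22 |
|---|---|---|---|
| Four infusions | 23/25 = 0.92 | 0.740 to 0.990 | 20.2 (16.3 to 21.8) |
| Four weekly treatments | 18/25 = 0.72 | 0.506 to 0.879 | 15.8 (11.1 to 19.3) |

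Section 1.5.2 also reports trial completion: 14 of 19 men and 2 of 6 women, so 16/25 = 0.64 and 0.64 × 22 = 14.1. Completion may include the later follow-up visits, so Week 4 attendance is the closer proxy for four weekly treatments.

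The intervals cover sampling error only. They do not cover the move from an all-active, four-dose-level study to a two-arm one.

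**4. Bias.** No estimate is possible. Phase 1b had no control arm. Its four adverse-event discontinuations were all for anaemia, and two patients died, one of febrile neutropenia and one of pancytopenia (Section 1.5.2.3). The dropout table (Table 6) was not in the text available for this review, so other reasons could not be checked.

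**The case against.** The strongest reply is that the intent is plain. Section 3.5 has the pharmacist "prepare the TK-112690 treatments by adding either active drug or placebo", so the drug's name there covers both arms. Section 5.2 says "The TK-112690/placebo dose will be 45 mg/kg", and the Synopsis keeps patients under observation "for a minimum of 25 hours post initial TK-112690 or placebo dose". By-group tables cannot be made without placebo patients. On this view two missing words are being treated as a lost control arm. The reading of intent is fair. But the same passages show that the authors usually name placebo when they mean both arms, and Section 10.2.1 does not. An operative definition should not depend on inference.

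On the unit, the infusion reading is better supported for this trial, since the only support for a weekly meaning comes from Phase 1b captions. That lowers the likely loss to about 2 of 22, though the interval allows about 6. It does not supply the missing definition.

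Three limits on the figures stand. The count of 11 is the planned number; List B in Section 3.5 could add 8 patients, with the split not given. The proxy pools dose levels, with 15 of the 25 patients at 60 mg/kg; the 45 mg/kg cohort alone went from 4 to 3 to 2 patients at Weeks 1, 2 and 4. The trial is also exploratory and its mucositis analysis descriptive, so the choice of efficacy set is a lesser matter than the missing arm.

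Some safeguards exist. Withdrawals, including those for adverse events, are summarised by group (Sections 10.3 and 10.3.1), and patients lost to follow-up are compared with the rest (Section 10.4). None of these brings an excluded patient's mucositis scores into the efficacy comparison.

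**Conclusion.** The concern holds. **Must fix:** as written, both sets are at most 11 against 0, which contradicts the primary objective and the by-group safety summaries. This follows from the wording and the saline placebo alone; it is probably a slip, but nothing else in the plan corrects it.

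**Should fix:** the four-dose rule has no unit and conditions on post-randomisation exposure. With placebo included, it would keep about 20 of 22 patients counted in infusions or about 16 counted in weeks, on the assumption that pooled Phase 1b attendance carries over to both arms. The size and direction of any bias in the treatment difference are unknown.

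**What to change.** Replace Section 10.2.1 with:

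> Efficacy population: all randomised patients who received at least one infusion of TK-112690 or placebo, analysed as randomised, using every available post-baseline mucositis assessment, including the one at withdrawal (Section 8.2). Safety population: all patients who received at least one infusion of TK-112690 or placebo, analysed as treated.

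Count an infusion once it has started. List by arm any patient replaced under Section 10.1.2; a patient who started but did not complete first dosing stays in, so the sets could exceed 22. If a four-dose set is wanted, define it for both arms in stated units (infusions or weeks) and use it as a sensitivity analysis only.

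The cost is two sentences, one listing and one extra analysis. Mucositis is already scored at scheduled visits (Table 12) and at withdrawal (Section 8.2), so no new data or patients are needed. The drawback is that partly exposed patients may dilute the contrast; the documents give no basis for saying by how much. The edit settles who is analysed, not how the four scales are summarised.
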